#### **6.6 Breaking the Blind**

At the initiation of the study, the study site will be instructed on the method for breaking the blind. The method will be an electronic process.

Property of Haleon- Confidential

May not be used, divulged, published or otherwise disclosed without the consent of Haleon

The electronic system will be programmed with blind-breaking instructions. In case of an emergency, the investigator has the sole responsibility for determining if unblinding of a subject's product assignment is warranted. Subject safety must always be the first consideration in making such a determination. If the investigator decides that unblinding is warranted, the investigator should make every effort to contact the sponsor prior to unblinding a subject's product assignment unless this could delay emergency treatment of the subject.

If a subject's product assignment is unblinded, the sponsor must be notified within 24 hours after breaking the blind. The date and reason that the blind was broken must be recorded in the source documentation and case report form, as applicable.

Any AE associated with breaking the blind must be recorded and reported as specified in this protocol. The study site may also be required to inform the Institutional Review Board (IRB) if the blind is broken.

## 6.7 Compliance

To facilitate subject compliance with product usage requirements:

- First use of their assigned study dentifrice will be carried out under supervision at the study site at the end of the screening visit (Visit 1) and additionally at Visit 2; study staff will demonstrate the correct amount of dentifrice to dispense and how to use the timer to ensure a 2-minute brushing time. Subjects will be provided with a diary at Screening (Visit 1) to record each completed brushing.
- First use of the peroxide tooth bleaching procedure will be carried out under supervision at the study site at Visit 2; study staff will demonstrate the application of the bleaching gel according to manufacturer's instructions. Subjects will be provided with a diary to record each completed tooth bleaching treatment.
- Subjects will attend each study visit with all tubes of dentifrice provided (used and unused) for a visual check of product usage, and with their completed diary for review by study staff. Any suspected over or under use, the number of any missed or additional brushings will be documented as deviations in the CRF; subjects will be re-instructed in the correct use of product and diary completion, as required.
- Subjects will also use the diary to note any issues with their study product, any oral problems, illnesses and new medications/ treatments. Details relevant to safety or efficacy should be reviewed by the investigator (or suitably qualified designee) and transcribed to the CRF, as appropriate; AEs must be documented in the CRF.

The number of any missed or additional applications or doses will be captured as protocol deviations. Subjects will be re-instructed in the correct usage requirements and diary completion as needed.

A record of the number of dentifrice tubes dispensed to and taken by each subject must be maintained and reconciled with study intervention and compliance records. Intervention start and stop dates, including dates for intervention delays and/or dose reductions will also be recorded in the CRF.

## 6.8 Concomitant Medication/Treatment(s)

Any medications, treatments or vaccine (including over-the-counter or prescription medicines, vitamins, and/or herbal supplements) taken during the study, from signing the informed consent, must be recorded in the CRF with indication, reason for use, unit dose, daily dose, and start and

Property of Haleon- Confidential

May not be used, divulged, published or otherwise disclosed without the consent of Haleon

stop dates of administration. All subjects will be questioned about medications/treatments at each site visit.

Medication/treatments taken 28 days prior to signing the informed consent form and until first study product application will be documented as a prior medication/treatment. Medications/treatments taken after first study product application will be documented as concomitant medication/treatments.

## **7 DISCONTINUATION OF STUDY INTERVENTION AND SUBJECT DISCONTINUATION/WITHDRAWAL**

### **7.1 Subject Discontinuation/Withdrawal**

A subject may withdraw from the study at any time at his or her own request or may be withdrawn at any time at the discretion of the investigator or sponsor for safety, behavioral reasons, or the inability of the subject to comply with the protocol-required schedule of study visits or procedures.

The following circumstances require discontinuation of study product and/or premature subject withdrawal:

- Protocol violation that may impact the subject's safety
- Withdrawal of informed consent
- Subject lost to follow-up
- Unblinding of the subject
- Pregnancy

If a subject is discontinued or prematurely withdraws from the study, the reason(s) for discontinuation or withdrawal and the associated date must be documented in the relevant section(s) of the CRF.

### **7.2 Lost to Follow up**

If a subject fails to return to the site for a required study visit the site must attempt to contact the subject and reschedule the missed visit as soon as possible and counsel the subject on the importance of maintaining the assigned visit schedule and ascertain whether the subject wishes to and/or should continue in the study.

A subject will be considered lost to follow up if he or she repeatedly fails to return for scheduled visits and is unable to be contacted by the study site. Before a subject is deemed lost to follow up, the investigator or designee must make every effort to regain contact with the subject (where possible, 3 telephone calls and, if necessary, a certified letter to the subject's last known mailing address or local equivalent methods). These contact attempts should be documented. If contact is made with the subject, the investigator should inquire about the reason for withdrawal, request that the subject return all products that they had been dispensed and if appropriate request that the subject return for a final visit and follow-up with the subject regarding any unresolved adverse events (AEs).

Final safety assessments may be carried out when the subject returns to the study site, at the investigator's discretion, which could include OST and OHT examinations.

Should the subject continue to be unreachable, he/she will be considered to have withdrawn from the study and lost to follow up.

Property of Haleon- Confidential

May not be used, divulged, published or otherwise disclosed without the consent of Haleon

Lack of completion of all or any of the early termination procedures will not be viewed as protocol deviations so long as the subject's safety was preserved.

If the subject withdraws from the study and withdraws consent for disclosure of future information, no further evaluations should be performed, and no additional data should be collected. The sponsor may retain and continue to use any data collected before such withdrawal of consent.

## 8 STUDY PROCEDURES

This section lists the procedures to be completed at each planned study visit. The timing of each procedure is listed in the Schedule of Activities section.

Adherence to the study design requirements, including all procedures are essential and required for study conduct.

### 8.1 Visit 1/Screening

Screening procedures will be conducted by the Investigator, or suitably qualified designee.

The following screening procedures will be completed, in the following order (wherever possible), and the findings recorded in the CRF. To facilitate subject flow, clinical assessments may be recorded on a paper source document and later transcribed into the CRF.

1. Informed Consent.
2. Demographics.
3. Review of medical history (including smoking/tobacco use status) and prior/concomitant medication/treatment.
4. OST and OHT examinations.
5. Assessment of tooth color and extrinsic tooth stain.
6. For subjects with a self-reported history of DH, assessment of DH, including EAR, MGI and tooth mobility assessments and Evaporative (Air) Sensitivity Assessment (Schiff sensitivity score).
7. Review of the inclusion/exclusion criteria.
8. Subject eligibility assessed. Subjects who do not meet the criteria for participation will be discontinued.
9. Qualifying subjects will be stratified and randomized to treatment groups.
10. Subject completes the tooth sensitivity questionnaire at site.
11. Study products will be dispensed, including sundry items, and diary.
12. Instruct subject in product usage requirements/diary completion and demonstrate dispensing ribbon of dentifrice on to toothbrush head; supervise first brushing and first diary entry.
13. AEs and incidents recorded.

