### **8.2.2 Visit 3/ End of tooth bleaching**

Procedures will be conducted by the Investigator, or suitably qualified designee.

Subjects will undergo, in the following order (wherever possible).

1. Changes in concomitant medication or non-drug treatments/procedures will be documented.
2. Spontaneous reporting of adverse events and those elicited by asking subjects to respond to a non-leading question such as “How do you feel?” will be assessed.
3. Subject will return study products and diary for visual inspection to evaluate product compliance and adherence to protocol.
4. Subject undergoes an OST examination.
5. Subject undergoes assessment of tooth color (Vita Shade) and extrinsic tooth stain (MLSI).
6. Subject completes the tooth sensitivity questionnaire.
7. Subject completes post-whitening questionnaire.
8. AEs and incidents recorded.

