### 9.1.3.4 Evaporative (Air) Sensitivity Assessment (Schiff sensitivity score)

The Evaporative (air) Sensitivity Assessment will be assessed for teeth that will be peroxide bleached and that exhibit none of the dentition exclusion criteria for tooth DH (Section 9.1.3), which show signs of EAR, which have an MGI=0 directly adjacent to the exposed dentine and which have clinical mobility = 0 only.

The examiner will apply an evaporative air stimulus by directing a maximum one second application of air from a dental air syringe to the exposed dentine surface from a distance of approximately 1 cm. The subject response will be scored using the Schiff Sensitivity scale immediately following the evaporative air stimulus. The Schiff Sensitivity scale is an examiner based index ([Schiff et al., 1994](#)) focusing on a combination of specific, observable, physical, behavioural and verbal responses from the subject as a result of the stimulation of exposed dentine, rather than solely an oral request from the subject to discontinue stimulation and may facilitate discrimination. The examiner will indicate the subject's response to the evaporative

Property of Haleon- Confidential

May not be used, divulged, published or otherwise disclosed without the consent of Haleon

air stimulus, after the stimulation of each individual tooth, using the Schiff Sensitivity scale as below.

Score	Subject Response
0	Subject does not respond to air stimulation
1	Subject responds to air stimulus but does not request discontinuation of stimulus
2	Subject responds to air stimulus and requests discontinuation or moves from stimulus
3	Subject responds to stimulus, considers stimulus to be painful, and requests discontinuation of the stimulus

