### 9.2.2 Macpherson Modification of the Lobene Stain Index (MLSI)

Extrinsic dental stain will be assessed on the facial surfaces of the 6 maxillary anterior teeth (6-11) [Universal tooth numbering system] at Visits 1-5), using the MacPherson modification ([Macpherson et al., 2000](#)) of the Lobene stain index ([Lobene, 1968](#)) (MLSI).

[figure not shown]
All assessments should be performed by a single, trained clinical examiner, with consistent lighting to standardize of the assessment conditions. If required, the examiner will brush the subject's anterior teeth with a wetted toothbrush and/or floss to remove any debris which could impact the accuracy of the stain assessment. Teeth will be air dried prior to and during the assessment as needed.

The facial surfaces of each assessable tooth is divided into four regions. The 'gingival' region is defined as a crescent-shaped band, approximately 2 mm wide, adjacent to the free margin of the gingiva and extending to the crest of the interdental papillae of the adjacent teeth. The 'body' of the tooth is then sub-divided into three regions on the facial surfaces.

The facial surfaces of each assessable tooth will be divided into 2 regions, with a total of 4 sites per tooth surface ([Figure 9-1](#)).

- **Gingival Region:** Defined as a crescent-shaped band (~ 2 mm wide) adjacent to the free margin of the gingiva and extending to the crest of the inter-dental papillae of the adjacent teeth (1 site).
- **Body Region:** The remainder of the tooth surface (the body) is further sub-divided into 3 sites.
  - Distal facial, body facial, mesial facial sites
  - Distal lingual, body lingual, mesial lingual sites

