**When completing this form please consider your experience over the last week**

[figure not shown]
Have your teeth been sensitive ? Y/N    **If NO do not complete any further questions.**

Please make a single vertical mark at the point on the line which represents the degree of overall tooth sensitivity (eg twinges, pain and other sensations in your teeth) that you have experienced **over the last week**

No Sensitivity \_\_\_\_\_ Extreme Sensitivity \_\_\_\_\_

**For Site use only:** \_\_\_\_\_ mm    \_\_\_\_\_ Initials

Please rate the **INTENSITY/DURATION/TOLERABILITY/DESCRIPTION** of your overall tooth sensitivity (eg twinges, pain and other sensations in your teeth) experienced over the past week. Mark the scales below with an "x" to indicate the best description of your sensitivity. Remember you can mark anywhere on the line, including between the descriptive words.

Final v1.0 16 Oct 15

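### At Visits 1 to 3 the sensitivity questionnaire follows examinations that put, or may put, air on the teeth; completing it first is a nearly free improvement

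*Protocol*

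**What the plan says.** Protocol section 9.2.3 gives the tooth sensitivity questionnaire at Visits 1 to 3 only. The form opens with "When completing this form please consider your experience over the last week" (Appendix 15.3). A Yes/No question comes first, and a subject who answers No completes nothing further.

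The Visit 1 list in section 8.1 runs in this order: "Assessment of tooth color and extrinsic tooth stain" (step 5), the DH assessments including the Schiff air test for subjects with self-reported DH (step 6), "Qualifying subjects will be stratified and randomized to treatment groups" (step 9), "Subject completes the tooth sensitivity questionnaire at site" (step 10), and "Study products will be dispensed, including sundry items, and diary" (step 11). Sections 8.2.1 and 8.2.2 place shade and MLSI at step 5 of Visits 2 and 3. The questionnaire comes after it, at step 7 of Visit 2 and, as "Subject completes the tooth sensitivity questionnaire", at step 6 of Visit 3. All three lists apply where the order can be followed. The narrative in protocol sections 1.1 and 4.1 gives the same sequence.

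Two of the preceding examinations involve air. For the MLSI, section 9.2.2 says "Teeth will be air dried prior to and during the assessment as needed". For the Schiff test, section 9.1.3.4 says "The examiner will apply an evaporative air stimulus by directing a maximum one second application of air from a dental air syringe", aimed at exposed dentine.

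**The concern.** Air on exposed dentine is the protocol's own way of provoking sensitivity. A subject who has felt it during the visit is then asked whether the teeth were sensitive over the past week, and how badly. The evoked sensation is not part of the week being rated, but it may influence the answer.

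The gate question is the most exposed item. A No that becomes a Yes raises the count of subjects with sensitivity, which section 12.3.3 of the protocol and section 4.4.3.1 of the SAP report by product and DH stratum. It also adds one more subject to the VAS, LMS and NRS summaries. If the added score is mild, the count rises while the mean among those scoring falls.

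What is at stake is the exploratory objective on sensitivity during bleaching, overall and within DH strata. Neither document plans to record whether a subject's teeth were dried, so the analysis could not adjust for it.

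**Working it through.** No figure in the plan attaches to this point, so the check is of sequence and of who is exposed.

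**Sequence** (step numbers from protocol sections 8.1 and 8.2.1 to 8.2.4)

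| Visit | Shade and MLSI (drying if needed) | Schiff air test | Randomisation | Questionnaire | Later steps |
|---|---|---|---|---|---|
| 1 | 5 | 6, self-reported DH only | 9 | 10 | dispensing 11, first brushing 12 |
| 2 | 5 | none | none | 7 | supervised brushing 9, first bleaching 11 |
| 3 | 5 | none | none | 6 | post-whitening questionnaire 7 |
| 4, 5 | 5 | none | none | not given | not relevant here |

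An examination in which air may be used therefore precedes the form at 3 of 3 questionnaire visits, which are 3 of the 5 study visits. The deliberate air stimulus precedes it at 1 of 3, in a subset.

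**Who receives air before the form**

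- *DH-positive stratum, Visit 1: certain.* Section 9.1.3 requires at least one tooth with a Schiff score of 2 or more. On the scale in section 9.1.3.4 that means the subject at least asked for the air to stop or moved away from it.
- *Self-reported DH not confirmed clinically, Visit 1: possible.* The air test is applied only to teeth that have passed the exclusion, exposed-dentine, gingival and mobility checks.
- *No self-reported DH, Visit 1: no Schiff test.* Drying for the MLSI only if needed.
- *All subjects, Visits 2 and 3:* drying for the MLSI only if needed.

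**Size of the first group.** Sections 4.2 and 5.4 expect enrolment to mirror a DH prevalence of 30 to 50%, and about 160 subjects are to be randomised:

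- 0.30 × 160 = 48
- 0.50 × 160 = 80

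This counts subjects exposed. It does not measure how far their scores move.

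**Which summaries are comparable.** Visits 2 and 3 share the same order and neither includes the Schiff test, so the scores before and after bleaching are collected under like conditions, apart from discretionary drying. Visit 1 differs from both in the DH-positive stratum. SAP section 4.4.3.1 tabulates the scores at each time point by product within strata, so the Visit 1 values will stand beside the other two.

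**The case against.** The case on the other side is substantial, and most of it limits the point.

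- *The form asks for weekly recall.* Section 9.2.3 directs subjects to the preceding seven days and has staff demonstrate correct completion. This stands as a safeguard. It makes an effect of same-day air uncertain, but does not exclude it, above all for a Yes/No gate.
- *Drying is conditional.* At Visits 2 and 3 the documents do not establish that any given subject had air on the teeth. This stands.
- *No bias between arms.* The Schiff test precedes 1:1 randomisation stratified by DH status, and the order is the same in both arms. This stands. A reader might infer that a product meant to relieve sensitivity would blunt the response to drying at Visits 2 and 3, so that part of any difference between arms arises in the clinic. That is conceivable, but nothing in the documents shows it.
- *No change from Visit 1 is planned.* A reader might infer that the order will produce a spurious improvement from Visit 1 in the DH-positive stratum. SAP section 3.1 rules out change-from-baseline assessments, and SAP section 4.4.3.1 gives these scales descriptive statistics only. What remains is that the Visit 1 column in that stratum is not like for like with the others.
- *Randomisation before the Visit 1 form.* A reader might take this as a compromised baseline. No product is dispensed until step 11 or used until step 12, and nothing says that subjects learn their allocation sooner. It is not a demonstrated problem.
- *Asking first might prime the Schiff response.* This is speculative and minor, since the subjects who receive the test have already reported a history of DH.

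**Conclusion.** The point holds as a minor, avoidable weakness in the order of procedures at the three questionnaire visits. Air may have been applied before every completion of the form. It certainly has been for every DH-positive subject at Visit 1, some 48 to 80 of 160 if enrolment follows the expected prevalence. Whether and how far the answers shift cannot be estimated from the documents, so it would be wrong to say that the scores are contaminated.

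The conclusion assumes that sites follow the listed order and that a sensation felt in the clinic can influence a seven-day recall answer. It reaches only the exploratory sensitivity summaries. Study success rests on VITA shade at 24 weeks, which is unaffected.

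**What to change.** In protocol sections 8.1, 8.2.1 and 8.2.2, have the questionnaire completed before any oral examination. At Visit 1 it would come after consent, demographics and history (after step 3) and before the soft and hard tissue, shade, MLSI and Schiff assessments, and hence also before randomisation. At Visits 2 and 3 it would come before the soft tissue, shade and MLSI examinations. Align the narrative in protocol sections 1.1 and 4.1, and in SAP section 1.1, which repeats the Visit 1 order.

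The cost is renumbering and a short form completed by screen failures at Visit 1 and by any subject not continued at Visit 2. Neither group would enter the planned tables: screen failures are not randomised, and the mITT population requires a shade assessment after bleaching. No extra visit, sample size or analysis change is needed.

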#### 8.1.1 Screening Procedures

##### 8.1.1.1 Informed Consent

The investigator, or designee, must obtain informed consent from each subject participating in this study after adequate explanation of the aims, methods, objectives, and potential hazards of

Property of Haleon- Confidential

May not be used, divulged, published or otherwise disclosed without the consent of Haleon

the study. An ingredients listing for the study dentifrices and peroxide tooth bleaching kit will be provided to each subject during the consent process to enable them to confirm they are not aware of any allergy or hypersensitivity to any of the ingredients listed. Two copies of the informed consent form (ICF) will be signed and dated by the subject, the subject will retain one copy and the other will be kept at site.

The investigator, or designee, must also explain to the subjects that they are completely free to refuse to enter the study or to withdraw from it at any time. Appropriate forms for documenting a signed and dated consent will be provided by either the investigator or by the sponsor.

The investigator, or designee, should sign and date each copy of the ICF to confirm that the consent process was completed correctly after the subject has signed.

The time the subject signed the ICF will be captured as this is the point from which all AEs will be captured. The date and time of consent will be recorded in the CRF.

If, during a subject's participation in the study, any new information becomes available that may affect the subject's willingness to participate in the study, each ongoing subject should receive a copy of this new information and be re-consented into the study. Each subject should be provided with a copy of the signed and dated amended consent form. The date of re-consent will be recorded on the CRF.

After signing the ICF, subjects will undergo the screening assessments to confirm that they meet all the inclusion criteria and none of the exclusion criteria. If the subject is confirmed eligible by the investigator (or designee) to participate in the study the subject is considered enrolled in the study.

